Event	Action to Be Taken
Symptomatic LVEF decrease from baseline	
	
Withhold cobimetinib for at least 4 weeks. Continue atezolizumab and vemurafenib.Patient referral to cardiologist is strongly recommended.Re-evaluate LVEF at 28 days. 
If the patient is asymptomatic following the treatment break:
 
If patient has a < 10% absolute decrease from baseline in LVEF, for the first occurrence resume cobimetinib with dose reduced by one level to 40 mg; for the second occurrence, resume cobimetinib at 20 mg; and for the third occurrence, permanently discontinue cobimetinib ^a. For all patients restarting treatment, re-evaluate LVEF at 2, 4, 10, and 16 weeks and then every 12 weeks (3 cycles as per protocol) or as clinically indicated until treatment discontinuation.If patient has an LVEF of < 40% or a ≥ 10% absolute decrease from baseline, permanently discontinue cobimetinib. 
If the patient remains symptomatic following the treatment break:
 
Permanently discontinue cobimetinib. 
For patients (asymptomatic and symptomatic) who permanently discontinue cobimetinib:
 
LVEF assessments should continue post-treatment every 6 weeks or as clinically indicated until the LVEF recovers to LLN or 50% and or symptoms resolve.

LLN = lower limit of normal; LVEF = left ventricular ejection fraction.

- ^a If corticosteroids have been initiated, they must be tapered over ≥ 1 month to ≤ 10 mg/day oral prednisone or equivalent before atezolizumab can be resumed.
- ^b Atezolizumab may be withheld for a period of time beyond 12 weeks to allow for corticosteroids to be reduced to ≤ 10 mg/day oral prednisone or equivalent. The acceptable length of the extended period of time must be based on an assessment of the benefits and risks by the investigator and in alignment with the protocol requirements for the duration of treatment and documented by the investigator. The Medical Monitor is available to advise as needed.
- ^c Resumption of atezolizumab may be considered in patients who are deriving benefit and have fully recovered from the immune-mediated event. The decision to re-challenge patients with atezolizumab should be based on *the investigator's benefit–risk assessment* and documented by the investigator (or an appropriate delegate). The Medical Monitor is available to advise as needed.

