- ^d Patients on a cobimetinib dose less than 60 mg will reduce by one dose level reduction (a 20-mg daily reduction), from a 40-mg daily dose to a 20-mg daily dose, and patients on a 20-mg daily dose at the time of the interruption (for LVEF decline) should discontinue cobimetinib.

Table 3 Guidelines for Management of Patients Who Experience Specific Adverse Events (cont.)

Event	Action to Be Taken
Rhabdomyolysis or CPK elevation	
General guidance	
 Consider withholding cobimetinib while investigating etiology. Continue atezolizumab and vemurafenib. Assess patient for any history of strenuous physical activity, blunt trauma, or recent intramuscular injections. Evaluate for cardiac injury and rhabdomyolysis. If evidence of clinically significant cardiac injury or rhabdomyolysis, consider permanent discontinuation of cobimetinib.
Asymptomatic CPK elevation, Grade 1, 2, or 3	
 Continue all study treatment.
Rhabdomyolysis or symptomatic CPK elevation, Grade 1, 2, or 3	
 Withhold cobimetinib. Continue atezolizumab and vemurafenib. If event improves by at least one grade within 28 days, resume cobimetinib with dose reduced by one level. If not, permanently discontinue cobimetinib.
Rhabdomyolysis or CPK elevation (symptomatic or asymptomatic), Grade 4	
 Withhold cobimetinib. Continue atezolizumab and vemurafenib. If event improves to Grade ≤ 3 within 28 days, resume cobimetinib with dose reduced by one level. If not, permanently discontinue cobimetinib.
Grade 3 or 4 or intolerable Grade 2 treatment-related toxicities not described above	
 Withhold all study treatment. If event resolves to Grade 1 or better within 12 weeks, resume atezolizumab at fixed dose. If not, permanently discontinue atezolizumab.^{a,b,c} If event resolves to Grade 1 or better within 28 days, resume cobimetinib and vemurafenib with doses reduced by one level. If not, permanently discontinue cobimetinib and vemurafenib.

CPK = creatine phosphokinase.

^a If corticosteroids have been initiated, they must be tapered over ≥ 1 month to ≤ 10 mg/day oral prednisone or equivalent before atezolizumab can be resumed.

^b Atezolizumab may be withheld for a period of time beyond 12 weeks to allow for corticosteroids to be reduced to ≤ 10 mg/day oral prednisone or equivalent.

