MRI = magnetic resonance imaging.

- ^a Atezolizumab may be withheld for a longer period of time (i.e., > 12 weeks after event onset) to allow for corticosteroids (if initiated) to be reduced to ≤ 10 mg/day oral prednisone or equivalent. The acceptable length of the extended period of time must be based on *the investigator's* benefit–risk *assessment* and in alignment with the protocol requirements for the duration of treatment and documented by the investigator. The Medical Monitor is available to advise as needed.^b If corticosteroids have been initiated, they must be tapered over ≥ 1 month to ≤ 10 mg/day oral prednisone or equivalent before atezolizumab can be resumed.
- ^c Resumption of atezolizumab may be considered in patients who are deriving benefit and have fully recovered from the immune-mediated event. The decision to re-challenge patients with atezolizumab should be based on *the* investigator's benefit–risk *assessment* and documented by the investigator. The Medical Monitor is available to advise as needed.

Appendix 10
Risks Associated with Atezolizumab
and Guidelines for Management of Adverse Events Associated
with Atezolizumab (cont.)

OCULAR EVENTS

Management guidelines for ocular events are provided in Section [5.1.5.4](#).

IMMUNE-MEDIATED CARDIAC EVENTS

Management guidelines for cardiac events are provided in [Table 2](#).

IMMUNE-MEDIATED MYOCARDITIS

Immune-mediated myocarditis should be suspected in any patient presenting with signs or symptoms suggestive of myocarditis, including, but not limited to, laboratory (e.g., B-type natriuretic peptide) or cardiac imaging abnormalities, dyspnea, chest pain, palpitations, fatigue, decreased exercise tolerance, or syncope. Myocarditis may also be a clinical manifestation of myositis *or associated with pericarditis* (*see section on pericardial disorders below*) and should be managed accordingly. Immune-mediated myocarditis needs to be distinguished from myocarditis resulting from infection (commonly viral, e.g., in a patient who reports a recent history of gastrointestinal illness), ischemic events, underlying arrhythmias, exacerbation of preexisting cardiac conditions, or progression of malignancy.

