All patients with possible myocarditis should be urgently evaluated by performing cardiac enzyme assessment, an ECG, a chest X-ray, an echocardiogram, and a cardiac MRI as appropriate per institutional guidelines. A cardiologist should be consulted. An endomyocardial biopsy may be considered to enable a definitive diagnosis and appropriate treatment, if clinically indicated.

Patients with signs and symptoms of myocarditis, in the absence of an identified alternate etiology, should be treated according to the guidelines in [Table 2](#).

Appendix 10
Risks Associated with Atezolizumab
and Guidelines for Management of Adverse Events Associated
with Atezolizumab (cont.)

IMMUNE-MEDIATED PERICARDIAL DISORDERS

Immune-mediated pericarditis should be suspected in any patient presenting with chest pain and may be associated with immune-mediated myocarditis (see section on myocarditis above).

Immune-mediated pericardial effusion and cardiac tamponade should be suspected in any patient presenting with chest pain associated with dyspnea or hemodynamic instability.

Patients should be evaluated for other causes of pericardial disorders such as infection (commonly viral), cancer related (metastatic disease or chest radiotherapy), cardiac injury related (post myocardial infarction or iatrogenic), and autoimmune disorders, and should be managed accordingly.

All patients with suspected pericardial disorders should be urgently evaluated by performing an ECG, chest X-ray, transthoracic echocardiogram, and cardiac MRI as appropriate per institutional guidelines. A cardiologist should be consulted. Pericardiocentesis should be considered for diagnostic or therapeutic purposes, if clinically indicated.

Patients with signs and symptoms of pericarditis, pericardial effusion, or cardiac tamponade, in the absence of an identified alternate etiology, should be treated according to the guidelines in Table 2. Withhold treatment with atezolizumab for Grade 1 pericarditis and conduct a detailed cardiac evaluation to determine the etiology and manage accordingly.

Table 2 Management Guidelines for Immune-Mediated Cardiac Events

Event	Management
Immune-mediated myocarditis, Grade 1	
Refer patient to cardiologist.Initiate treatment as per institutional guidelines.

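### Table 3 continues atezolizumab without condition for symptomatic LVEF decrease, and acts only on cobimetinib if a CPK work-up finds cardiac injury, where Appendix 10 would suspect immune-mediated myocarditis

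*Protocol*

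**What the plan says.** **Symptomatic LVEF decrease (Protocol 5.1.5.4, Table 3).** The opening instruction is "Withhold cobimetinib for at least 4 weeks. Continue atezolizumab and vemurafenib". The row adds "Patient referral to cardiologist is strongly recommended" and a repeat LVEF at 28 days. After the break it distinguishes patients whose symptoms have resolved from those who remain symptomatic. Every action that follows concerns cobimetinib.

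**Rhabdomyolysis or CPK elevation, general guidance (same table).** The row begins "Consider withholding cobimetinib while investigating etiology. Continue atezolizumab and vemurafenib". It asks the site to evaluate for cardiac injury and rhabdomyolysis, then says "If evidence of clinically significant cardiac injury or rhabdomyolysis, consider permanent discontinuation of cobimetinib". It gives no further instruction on atezolizumab.

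**Appendix 10, immune-mediated myocarditis.** Suspicion is to be raised by suggestive laboratory findings or by "cardiac imaging abnormalities, dyspnea, chest pain, palpitations, fatigue, decreased exercise tolerance, or syncope". The response is prompt: "All patients with possible myocarditis should be urgently evaluated by performing cardiac enzyme assessment, an ECG", with chest X-ray, echocardiogram and cardiac MRI as appropriate, and a cardiology consultation. Where no alternate etiology is identified, Table 2 of the appendix applies. That table stops atezolizumab permanently for Grades 2 to 4. The myositis text in the same appendix names a creatine kinase rise as a diagnostic feature and asks for monitoring for myocarditis when myositis is possible.

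**The concern.** A symptomatic LVEF decrease is a cardiac imaging abnormality with symptoms, so one patient can meet both the Table 3 row and the Appendix 10 grounds for suspicion. The row presumes cobimetinib is the cause and continues atezolizumab without waiting for the work-up that would show whether it is. In the CPK row the cause is unknown by the row's own account, yet atezolizumab continues, and a finding of cardiac injury leads only to cobimetinib.

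At stake is patient safety. A patient with unrecognised myocarditis could receive further doses of a drug that the protocol stops permanently once Grade 2 to 4 myocarditis is recognised. The intent-to-treat comparison of PFS is not affected.

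**Working it through.** This is mainly a check of text against text. The plan states no figure to reproduce.

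**1. Do the triggers overlap?** For LVEF, yes: the row's heading describes an abnormal imaging result with symptoms, and Appendix 10 lists both kinds of sign. For CPK, the overlap is narrower. A CPK rise alone is a myositis feature. It is the finding of cardiac injury that brings the patient within the myocarditis text.

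**2. Does either row lead to a decision on atezolizumab?** No. In the LVEF row, symptoms that persist after the break lead only to permanent discontinuation of cobimetinib. Yet persistence off cobimetinib weakens the case that cobimetinib was the cause. In the CPK row, cardiac injury leads only to considering discontinuation of cobimetinib.

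**3. Where is a site sent?**
- Section 4.5.6.3 sends decreased LVEF to Section 5.1.2.2 and Table 3.
- Section 5.1.2.2 (LVEF) and Section 5.1.2.5 (CPK) send the site to Table 3. None of these three names Appendix 10.
- Section 5.1.1 reserves Appendix 10 for events associated only with atezolizumab, whereas left ventricular dysfunction is an identified cobimetinib risk (Section 5.1.2).
- Section 4.3.2.1 and the introduction to Table 3 in Section 5.1.5.4 do point to Appendix 10, in general terms.
- Neither row nor its footnotes mentions Appendix 10 or myocarditis. The infusion-reaction row of the same table does carry its own Appendix 10 pointer.

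**4. How does the protocol treat comparable uncertainty?**
- Pericarditis (Appendix 10): "Withhold treatment with atezolizumab for Grade 1 pericarditis and conduct a detailed cardiac evaluation to determine the etiology".
- Suspected Stevens-Johnson syndrome or toxic epidermal necrolysis (Table 3): atezolizumab is withheld on suspicion.
- Ocular events (Table 3): potentially immune-mediated events of Grade 2 lead to withholding. For events of Grade 2 or above, atezolizumab continues only under the heading for toxicity that is not immune related.

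**5. Possible exposure.** Inputs: atezolizumab 840 mg every 14 days (Section 4.3.2.1), LVEF re-check at 28 days (Table 3), and about 500 patients randomized 1:1 (Section 3.1).
- LVEF row followed alone: 28 / 14 = 2 scheduled infusions; 2 × 840 = 1680 mg.
- Work-up completed within 14 days: at most 14 / 14 = 1 infusion, 840 mg, and none if completed before the next infusion.
- Atezolizumab withheld during the work-up: 0.
- Patients assigned active atezolizumab (Arm B): 500 / 2 = about 250.

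The CPK general-guidance row gives no re-check time, so no dose count can be attached to it. The documents give no rate of myocarditis or symptomatic LVEF decrease, so no patient count follows.

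**The case against.** The strongest reply is that the two texts can be read in sequence. Section 5.1.5.4 applies interruptions to the component judged the primary cause and says Table 3 does not replace clinical judgment. Cobimetinib is a known cause of LVEF decrease, and Appendix 10 applies its treatment table only when no alternate etiology is identified. The LVEF row strongly recommends a cardiology referral, Section 4.5 requires an acceptable clinical assessment before each dose, and Section 5.1.5.3 allows atezolizumab to be suspended for treatment-related toxicity. All of this stands and lowers the risk. It does not remove the problem. Judging the primary cause needs the urgent work-up, which the row does not order, and the condition about alternate etiology governs treatment, not suspicion or evaluation.

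A second reply also stands: Appendix 10 does not itself tell sites to withhold atezolizumab while myocarditis is only suspected, and its Grade 1 myocarditis row only refers and treats. A reader might infer that Table 3 breaches an existing rule to withhold. It does not. The hold proposed here is a new instruction, supported by how the protocol handles comparable events.

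Third, most CPK elevations seen with cobimetinib were asymptomatic and resolved (Section 5.1.2.5), and the row asks for a cardiac evaluation every time. Withholding on any CPK rise, or on mere suspicion of injury, would be too broad.

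**Conclusion.** The concern holds for both rows. The LVEF row gives an unconditional instruction to continue atezolizumab and never returns to it. The CPK row leaves atezolizumab running even when cardiac injury is found. This is a stated rule that could lead to unsafe dosing, and it is cheap to correct.

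Three stronger readings are not supported:
- **That sites are never directed to Appendix 10.** Sections 4.3.2.1 and 5.1.5.4 do direct them there. The gap is in the rows and in the LVEF and CPK routing.
- **That two further doses are to be expected.** The 1680 mg figure assumes that a site follows the LVEF row alone and that the referral, the pre-dose assessment and the urgent work-up change nothing. It is an upper bound.
- **That Appendix 10 Table 2 also needs a cobimetinib and vemurafenib rule.** The Table 3 catch-all for "Grade 3 or 4 or intolerable Grade 2 treatment-related toxicities not described above" already withholds all study treatment, which leaves only tolerable Grade 2 myocarditis without a specific rule. The 28-day provision in Section 5.1.5.3 asks for Medical Monitor discussion only after more than 28 days off drug, so it would not support a general requirement for agreement before resuming.

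One limit remains: Section 5.1.4 on combination use is redacted in the public protocol, so any guidance given there could not be checked.

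**What to change.** **Symptomatic LVEF row.** Replace the instruction on atezolizumab and vemurafenib with: *Evaluate urgently for immune-mediated myocarditis per Appendix 10; withhold atezolizumab until the work-up identifies an alternate etiology, and manage per Appendix 10 Table 2 if none is identified; continue vemurafenib.*

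**CPK general-guidance row.** Apply the same wording only if the evaluation shows evidence of clinically significant cardiac injury. Otherwise leave the row as it is.

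Make no change to Appendix 10 Table 2.

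**Cost.** A wording amendment to two table rows. It adds no visits, tests or patients, because Appendix 10 already requires urgent evaluation of possible myocarditis. The downside is that some patients whose LVEF fall is due to cobimetinib would have atezolizumab or blinded placebo delayed, by roughly one dose per 14 days of work-up.

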5.1.1 Risks Associated with Atezolizumab

Atezolizumab has been associated with risks such as the following: infusion-related reactions and immune-mediated hepatitis, pneumonitis, colitis, pancreatitis, diabetes mellitus, hypothyroidism, hyperthyroidism, adrenal insufficiency, hypophysitis, Guillain-Barré syndrome, myasthenic syndrome or myasthenia gravis, *facial paresis*, *myelitis*, meningoencephalitis, myocarditis, *pericardial disorders*, nephritis, myositis, and severe cutaneous adverse reactions. *In addition*, immune-mediated reactions may involve any organ system and lead to hemophagocytic lymphohistiocytosis. Refer to Appendix 10 of the protocol and to Section 6 of the Atezolizumab Investigator's Brochure for a detailed description of anticipated safety risks for atezolizumab.

Guidelines for management of patients who develop specific adverse events associated with atezolizumab, vemurafenib, or cobimetinib are provided in Section 5.1.5.4 (see Table 3), and guidelines for events associated only with atezolizumab are provided in Appendix 10.

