
• Acute disseminated encephalomyelitis• Addison disease• Ankylosing spondylitis• Antiphospholipid antibody syndrome• Aplastic anemia• Autoimmune hemolytic anemia• Autoimmune hepatitis• Autoimmune hypoparathyroidism• Autoimmune hypophysitis• Autoimmune myelitis• Autoimmune myocarditis• Autoimmune oophoritis• Autoimmune orchitis• Autoimmune thrombocytopenic purpura• Behçet disease• Bullous pemphigoid• Chronic fatigue syndrome• Chronic inflammatory demyelinating polyneuropathy• Churg-Strauss syndrome	
• Dermatomyositis• Diabetes mellitus, Type 1• Dysautonomia• Epidermolysis bullosa acquisita• Gestational pemphigoid• Giant cell arteritis• Goodpasture syndrome• Graves disease• Guillain-Barré syndrome• Hashimoto disease• IgA nephropathy• Inflammatory bowel disease• Interstitial cystitis• Kawasaki disease• Lambert-Eaton myasthenia syndrome• Lupus erythematosus• Lyme disease, chronic• Meniere syndrome• Mooren ulcer• Morphea• Multiple sclerosis• Myasthenia gravis• Crohn disease	
• Neuromyotonia• Opsoclonus myoclonus syndrome• Optic neuritis• Ord thyroiditis• Pemphigus• Pernicious anemia• Polyarteritis nodosa• Polyarthritis• Polyglandular autoimmune syndrome• Primary biliary cirrhosis• Psoriasis• Reiter syndrome• Rheumatoid arthritis• Sarcoidosis• Scleroderma• Sjögren syndrome• Stiff-Person syndrome• Takayasu arteritis• Ulcerative colitis• Vitiligo• Vogt-Koyanagi-Harada disease• Granulomatosis with polyangiitis
---	---	---

Appendix 10

Risks Associated with Atezolizumab and Guidelines for Management of Adverse Events Associated with Atezolizumab

Toxicities associated or possibly associated with atezolizumab treatment should be managed according to standard medical practice. Additional tests, such as autoimmune serology or biopsies, should be used to evaluate for a possible immunogenic etiology.

Although most immune-mediated adverse events observed with immunomodulatory agents have been mild and self-limiting, such events should be recognized early and treated promptly to avoid potential major complications. Discontinuation of atezolizumab may not have an immediate therapeutic effect, and in severe cases, immune-mediated toxicities may require acute management with topical corticosteroids, systemic corticosteroids, or other immunosuppressive agents.

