Myositis or inflammatory myopathies are a group of disorders sharing the common feature of inflammatory muscle injury; dermatomyositis and polymyositis are among the most common disorders. Initial diagnosis is based on clinical (muscle weakness, muscle pain, skin rash in dermatomyositis), biochemical (serum creatine kinase increase), and imaging (electromyography/MRI) features, and is confirmed with a muscle biopsy. Patients with possible myositis should be referred to a rheumatologist or neurologist. Patients with possible myositis should be monitored for signs of myocarditis.

Patients with signs and symptoms of myositis, in the absence of an identified alternate etiology, should be treated according to the guidelines in [Table 5](#)

Appendix 10
Risks Associated with Atezolizumab
and Guidelines for Management of Adverse Events Associated
with Atezolizumab (cont.)

Table 5 Management Guidelines for Immune-Mediated Myositis

Event	Management
Immune-mediated myositis, Grade 1	
 • Continue atezolizumab. • Refer patient to rheumatologist or neurologist. • Initiate treatment as per institutional guidelines.
Immune-mediated myositis, Grade 2	
 • Withhold atezolizumab for up to 12 weeks after event onset ^a and contact Medical Monitor. • Refer patient to rheumatologist or neurologist. • Initiate treatment as per institutional guidelines. • Consider treatment with corticosteroids equivalent to 1–2 mg/kg/day IV methylprednisolone and convert to 1–2 mg/kg/day oral prednisone or equivalent upon improvement. • If corticosteroids are initiated and event does not improve within 48 hours after initiating corticosteroids, consider adding an immunosuppressive agent. • If event resolves to Grade 1 or better, resume atezolizumab. ^b • If event does not resolve to Grade 1 or better while withholding atezolizumab, permanently discontinue atezolizumab and contact Medical Monitor. ^c

^a Atezolizumab may be withheld for a longer period of time (i.e., > 12 weeks after event onset) to allow for corticosteroids (if initiated) to be reduced to the equivalent of ≤ 10 mg/day oral prednisone. The acceptable length of the extended period of time must be based on *the investigator's* benefit–risk *assessment* and in alignment with the protocol requirements for the duration of treatment and documented by the investigator. The Medical Monitor is available to advise as needed.

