^b If corticosteroids have been initiated, they must be tapered over ≥ 1 month to the equivalent of ≤ 10 mg/day oral prednisone before atezolizumab can be resumed.

^c Resumption of atezolizumab may be considered in patients who are deriving benefit and have fully recovered from the immune-mediated event. The decision to re-challenge patients with atezolizumab should be based on *the investigator's* benefit–risk *assessment* and documented by the investigator. The Medical Monitor is available to advise as needed.

Appendix 10
Risks Associated with Atezolizumab
and Guidelines for Management of Adverse Events Associated
with Atezolizumab (cont.)

Table 5 Management Guidelines for Immune-Mediated Myositis (cont.)

Event	Management
Immune-mediated myositis, Grade 3	
 • Withhold atezolizumab for up to 12 weeks after event onset^a and contact Medical Monitor. • Refer patient to rheumatologist or neurologist. • Initiate treatment as per institutional guidelines. • Respiratory support may be required in more severe cases. • Initiate treatment with corticosteroids equivalent to 1–2 mg/kg/day IV methylprednisolone, or higher-dose bolus if patient is severely compromised (e.g., cardiac or respiratory symptoms, dysphagia, or weakness that severely limits mobility); convert to 1–2 mg/kg/day oral prednisone or equivalent upon improvement. • If event does not improve within 48 hours after initiating corticosteroids, consider adding an immunosuppressive agent. • If event resolves to Grade 1 or better, resume atezolizumab.^b • If event does not resolve to Grade 1 or better while withholding atezolizumab, permanently discontinue atezolizumab and contact Medical Monitor.^c • For recurrent events, treat as a Grade 4 event. Permanently discontinue atezolizumab and contact the Medical Monitor.^c

^a Atezolizumab may be withheld for a longer period of time (i.e., >12 weeks after event onset) to allow for corticosteroids (if initiated) to be reduced to the equivalent of ≤ 10 mg/day oral prednisone. The acceptable length of the extended period of time must be based on *the investigator's benefit–risk assessment* by the investigator and in alignment with the protocol requirements for the duration of treatment and documented by the investigator. The Medical Monitor is available to advise as needed.

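### Table 3 continues atezolizumab in symptomatic CPK elevation or rhabdomyolysis while Appendix 10 withholds it for Grade 2–3 possible myositis, and the visible text does not say which applies before a cause is judged

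*Protocol*

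**What the plan says.** Protocol Section 5.1.5.4, Table 3, has four rows under rhabdomyolysis or CPK elevation.

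- General guidance: "Consider withholding cobimetinib while investigating etiology. Continue atezolizumab and vemurafenib". The work-up listed is exertion, trauma, intramuscular injections, cardiac injury and rhabdomyolysis. A finding of significant cardiac injury or rhabdomyolysis leads only to considering permanent discontinuation of cobimetinib.
- Asymptomatic elevation, Grades 1–3: all study treatment continues.
- Rhabdomyolysis or symptomatic elevation, Grades 1–3: "Withhold cobimetinib. Continue atezolizumab and vemurafenib".
- Grade 4, symptomatic or not: the same instruction.

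Appendix 10, on immune-mediated myositis, describes how the condition presents: "Initial diagnosis is based on clinical (muscle weakness, muscle pain, skin rash in dermatomyositis), biochemical (serum creatine kinase increase), and imaging (electromyography/MRI) features". Its trigger for the dosing table is: "Patients with signs and symptoms of myositis, in the absence of an identified alternate etiology, should be treated according to the guidelines" in Table 5. Table 5 continues atezolizumab at Grade 1. At Grades 2 and 3 it says "Withhold atezolizumab for up to 12 weeks after event onset". In the Grade 3 row it adds "For recurrent events, treat as a Grade 4 event", with permanent discontinuation.

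On scope, Section 5.1.1 sends events linked to any of the three drugs to Table 3, and says that "guidelines for events associated only with atezolizumab are provided in Appendix 10". Appendix 10 opens more widely: "Toxicities associated or possibly associated with atezolizumab treatment should be managed according to standard medical practice".

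**The concern.** Muscle pain or weakness with a raised CPK is how cobimetinib-related rhabdomyolysis can present. It is also how Appendix 10 describes myositis. The protocol classes rhabdomyolysis as a cobimetinib risk (Section 5.1.2) and myositis as an atezolizumab risk (Section 5.1.1). When such a patient is first seen, the cause is often not yet known.

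The two places have opposite defaults under that uncertainty. Table 3 continues atezolizumab while the cause is sought. Appendix 10 withholds it at Grades 2 and 3 unless another cause has been found. Two investigators with the same patient could each follow a written instruction and dose differently. Following the Table 3 rows literally means continuing a checkpoint inhibitor in a patient who may have immune-mediated myositis. Investigators are blinded (Section 4.2), so they cannot normally rule atezolizumab out by arm.

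**Working it through.** No arithmetic applies, and the plan has no figure to reproduce. The check sets the instructions side by side for a patient whose cause is still open, then asks whether any visible provision chooses between them.

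**Step 1. Compare the atezolizumab instructions.** CPK or rhabdomyolysis grade and myositis grade describe different things. The grades below are myositis grades, except in the first line.

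| Presentation, cause open | Table 3 | Appendix 10 Table 5 | Agree? |
|---|---|---|---|
| CPK elevation without muscle symptoms | Continue | Myositis rule not triggered | Yes |
| Raised CPK, muscle symptoms, Grade 1 | Continue | Continue | Yes |
| Raised CPK, muscle symptoms, Grade 2 | Continue | Withhold | No |
| Raised CPK, muscle symptoms, Grade 3 | Continue | Withhold | No |
| Recurrent Grade 3 | Continue | Permanently discontinue | No |

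The conflict is confined to the last three lines.

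**Step 2. Look for a link between the two places.** Of the four CPK rows, three say to continue atezolizumab and vemurafenib while cobimetinib is, or may be, withheld. None of the four names myositis or refers to Appendix 10. The myositis section of Appendix 10 does not refer back to the CPK rows. Other parts of Table 3 handle shared toxicities more explicitly:

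- The infusion-reaction row sends the reader to Appendix 10.
- Ocular events are split into potentially immune-mediated and not immune related.
- Grade 4 photosensitivity makes continuing atezolizumab conditional on clinical indication.

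**Step 3. Test each general provision against the open-cause period.**

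- *Section 5.1.1, routing by association.* This works once the event is attributed. Before that, its narrow scope for Appendix 10 leans towards Table 3, while Appendix 10's own opening covers events only possibly related to atezolizumab. The two scope statements pull apart.
- *Section 5.1.5.4, interrupting the drug held mainly responsible.* This needs a judgment of cause first.
- *Section 5.1.5.4, closing pointer to Section 5.1.1 and Appendix 10.* This covers events associated with atezolizumab, so it too depends on attribution.
- *Section 5.1.5.3, permission to suspend atezolizumab.* The trigger is toxicity related to study treatment as a whole, so it can be used before attribution. It allows a hold but does not rank the tables.
- *Section 4.5, toxicity check before each dose.* This is a real safeguard, but what counts as acceptable is left to the investigator, whose event-specific row says to continue.
- *Section 5.1.5.4, clinical-judgment clause.* This lets the investigator depart from Table 3 but leaves both instructions standing.

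None of these says which instruction applies before a cause is judged.

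**The case against.** The strongest reply is that the protocol already gives the investigator enough. Table 5 does not require confirmed attribution, and Appendix 10 sends possible myositis to a rheumatologist or neurologist and asks for monitoring for myocarditis. Its myocarditis guidance permanently discontinues atezolizumab at Grades 2–4. The text just above Table 3 points to Appendix 10. Section 5.1.5.3 gives written authority to hold atezolizumab without first blaming it. Holding cobimetinib first is a defensible default, since rhabdomyolysis is a named cobimetinib risk and every patient takes that drug. All of this stands, and it keeps the risk small. It does not remove the opposite instruction in the row the investigator is most likely to open.

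Two stronger readings are tempting, and the documents do not support them.

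- A reader might infer that no rule at all governs the choice. That goes too far: Sections 5.1.1 and 5.1.5.4 settle it once a cause is judged. Section 5.1.4, on combination use, is also redacted, so only the visible text can be described as silent.
- A reader might infer that, with infusions every 2 weeks, the 28-day limit in the CPK rows implies two atezolizumab doses given during undiagnosed myositis. The 28 days are the recovery limit for resuming cobimetinib. They do not describe how long the cause stays unknown, and every dose is subject to the check in Section 4.5.

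**Conclusion.** The point holds for one group: patients with raised CPK and muscle symptoms that would be myositis Grade 2 or 3 (including recurrent Grade 3), before a cause is judged. In that interval the visible text gives opposite atezolizumab instructions and does not rank them. There is no conflict at myositis Grade 1 or for CPK elevation without symptoms.

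This is a dosing-safety clarity point of limited risk. It should be corrected, but it is not urgent. No efficacy analysis is affected. Only Arm B receives active atezolizumab. The documents give no frequency for such cases, and Section 5.1.2.5 reports that most CPK elevations were asymptomatic and resolved, so no number of patients or infusions is claimed. The conclusion assumes that the redacted Section 5.1.4 does not rank the two instructions, which cannot be checked.

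**What to change.** In the general-guidance row, the symptomatic Grade 1–3 row and the Grade 4 row of Table 3, leave the vemurafenib instruction as it is and replace the unqualified atezolizumab instruction with:

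*Continue atezolizumab unless immune-mediated myositis (Grade 2 or higher) or myocarditis is suspected with no alternate etiology identified; if so, manage atezolizumab per Appendix 10 Table 5 or Table 2.*

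Add myositis to the work-up list in the general-guidance row.

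This is a wording change in three rows plus one added item, with no new scheduled procedure. Table 3 already refers to Appendix 10 for infusion reactions. The downside is an occasional delayed atezolizumab or placebo infusion in a patient whose event turns out to be due to cobimetinib.
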